#### **8.1.8.8 EQ-5D-5L**

The EQ-5D-5L will be used to explore the impact of treatment and disease state on health state utility.

The EQ-5D-5L, developed by the EuroQoL Group, is a generic questionnaire that provides a simple descriptive profile of health and a single index value for health status for economic appraisal ([EuroQol 2019](#)). The EQ-5D-5L questionnaire comprises 6 questions that cover 5 dimensions of health (mobility, self-care, usual activities, pain/discomfort, and anxiety/depression) over 5 levels of increasing severity (“no problems,” “slight problems,” “moderate problems”, “severe problems”, and “extreme problems”). Participants indicate their current health state by selecting the most appropriate level in each of the 5 dimensions.

Respondents also assess their health today using the EQ-VAS, which ranges from 0 (worst imaginable health) to 100 (best imaginable health).

A copy of the scale is provided in Appendix [G 8](#).

#### **8.1.8.9 Administration of ePRO Questionnaires**

Participants will complete a daily e-Diary using a hand-held device at home to capture:

- PN pain intensity (assessed using the PAINS-pNF)
- PN pain medication use
- Drug diary to record whether study intervention was taken as instructed

For all other ePRO assessments including PII-pNF, PGIC, PGIS, PROMIS physical function items, PlexiQol, Peds QL (NF1 module-adult form) Skin Sensations domain, and EQ-5D-5L, participants will perform the ePRO assessments using an electronic tablet during clinic visits at the time points indicated in the SoA.

Each site must allocate the responsibility for the administration of the ePRO instruments to a specific individual (eg, a research nurse or study co-ordinator) and, if possible, assign a backup person to cover if that individual is absent.

Approximately 10 to 20 minutes is required for participants to complete the questionnaires.

The below instructions should be followed when collecting PRO data via an electronic device:

- The PRO questionnaires should be completed prior to any other study procedures or discussions (following informed consent) that could bias the participant’s responses to the questions.
- At site visits, when each instrument is due to be completed, the following order should be observed:
  - Patient Global Impression of Severity (PGIS)
  - Patient Global Impression of Change (PGIC)
  - Pain Interference Index Plexiform Neurofibroma (PII-pNF)

- Patient reported Outcomes Measurement Information System (PROMIS physical function items)
  - Paediatric Quality of Life Inventory (PedsQL NF1 module acute Version 3.0 – adult report) Skin Sensations domain
  - Plexiform Neurofibromas Quality of Life Measure (PlexiQoL)
  - EuroQol 5-Dimension 5-level (EQ-5D-5L)
- The PRO questionnaires should be completed by the participant in a quiet and private location.
- The participant should be given sufficient time to complete the PRO questionnaires at his/her own speed.
- The research nurse or appointed site staff should explain to participants the value and relevance of these data so they are motivated to comply with questionnaire completion.
- The research nurse or appointed site staff should stress that the information is not routinely shared with study staff. Therefore, if the participant has any medical problems, he/she should discuss them with the doctor or research nurse separately from the ePRO assessment.
- The research nurse or appointed site staff must train the participant on how to use the ePRO device using the materials and training provided by the ePRO vendor.
- The research nurse or appointed site staff must provide guidance on whom to call if there are problems with the device when the participant is completing the ePRO at home.
- All questionnaires must be completed using the ePRO device. Paper questionnaires may be allowed in this study under exceptional circumstances (eg, an IT system failure or breakage of electronic device).
- The research nurse or appointed site staff must remind participants that there are no right or wrong answers and avoid introducing bias by not clarifying items.
- The participant should not, wherever possible, receive help from relatives, friends, or clinic staff to read or complete the ePRO questionnaires. However, if the participant has motor or reading difficulties that will prevent them from using the e-Device, the items may be read aloud or responses selected on the e-Device. Any person providing assistance must be informed by site staff that they must not influence the participant's responses in any way and responses selected on the e-Device on behalf of the participant must follow the answer provided by the participant aloud.
- Site staff must administer questionnaires available in the language that the participant speaks and understands. Questions must not be read in an available language and translated into another language for the participant.

- It is vital that the ePRO reporting is initiated as specified in the SoA to capture the effect of study intervention.
- Reminders should be sent to participants at home as needed to ensure compliance with the assessment schedules.
- Finally, the research nurse or appointed site staff will review the completion status of questionnaires during site visits, and document the reason(s) why a participant could not complete assessments, in the source documents and in the designated eCRF. If a participant's compliance drops to or below 85%, they will be flagged in the routine compliance report generated by the ePRO system, and appropriate action will be taken (eg, discussion with participant to improve compliance, a check in call from the site to ask the participant if they have any difficulties in completing questionnaires on schedule, etc). Whilst site staff will be able to monitor compliance they will remain blinded to the PAINS-pNF scores (except in exceptional circumstances when paper copies are used).
- In the event that the ePRO device cannot be used (ie, technical failure, lost device, etc) and there is a back-up platform available for the PRO questionnaire, the participant will complete it on a website following the same steps as outlined above.

#### **8.1.8.10 Qualitative Participant Interviews**

Qualitative interviews will be performed in approximately 36 trial participants at baseline and at 2 other timepoints during the trial. During the baseline interviews, trial participants will be asked a series of questions to better understand their experience with PN symptoms and any associated impacts. Interviews over the course of the trial will focus on any changes to experienced PN symptoms and impacts. A semi-structured interview guide will be provided in the separate interview study manual. These interviews will be conducted by trained independent moderators in selected countries. Participation in these interviews is optional, and subjects must indicate willingness to participate in the informed consent form. The interview results will be reported separately from the clinical study report.

## **8.2 Safety Assessments**

Planned time points for all safety assessments are provided in the SoA.

#### **8.2.1 Physical Examinations**

- A full physical examination will be performed and include assessments of the following; general appearance, respiratory, cardiovascular, abdomen, skin, head and neck (including ears, eyes, nose and throat), lymph nodes, thyroid, musculoskeletal (including spine and extremities), urogenital, dermatological, gastrointestinal, endocrine, haematologic/lymphatic, and neurological systems.
- Targeted physical examinations are to be used by the investigator on the basis of clinical observations and symptomatology. A targeted physical examination will include, at a

minimum, assessments of the general appearance, respiratory and cardiovascular systems, skin and abdomen (liver and spleen).

Physical examination, as well as assessment of height and weight, will be performed at timepoints as specified in the SoA; investigators should pay special attention to clinical signs related to previous serious illnesses, new or worsening abnormalities may qualify as AEs, see Section 8.3.5 for details.

If unexplained muscle weakness or myalgia (muscle pain) occurs, the participant should have a neuromuscular examination, urine analysis and CK measurement performed (with an additional CK-MM isoform measurement where possible) and be managed according to local practice.

### **8.2.2 Height and Weight**

Height and weight will be measured at the timepoints outlined in the SoA. The participant's height will be recorded in cm and weight will be recorded in kg. Height and weight measurements will be performed in light clothing and with shoes off.

Height: The participants should take off shoes and heels should be placed against a wall with ankles together. Height should be measured in a standing position with a stadiometer. In participants with known leg length discrepancy due to limb hypertrophy, height should be measured with the participant bearing weight on the limb without hypertrophy.

Body Surface Area should be calculated using the formula derived by Mosteller:

- Mosteller:  $\sqrt{(\text{weight (kg)} \times \text{height (cm)}) / 3600}$

### **8.2.3 Vital Signs**

Vital signs will be performed at timepoints as specified in the SoA.

Temperature, (same method to be used throughout the study), pulse rate, oxygen saturation by pulse oximetry, respiratory rate and BP will be assessed.

Blood pressure and pulse measurements will be assessed in a sitting position with a completely automated device. Manual techniques will be used only if an automated device is not available.

Blood pressure and pulse measurements should be preceded by at least 5 minutes of rest for the participant in a quiet setting without distractions (eg, television, cell phones). The average of 3 BP readings, taken consecutively at intervals of at least one minute apart will be recorded in the eCRF.

Situations in which vital signs results should be reported as AEs are described in Section [8.3.5](#).

#### **8.2.4      ECGs**

Single 12-lead ECGs will be performed at timepoints as specified in the SoA after the participant has been resting semi-supine for at least 5 minutes and recorded while the participant remains in that position using an ECG machine that automatically calculates the heart rate and measures PR, QRS, QT, and QT interval corrected by Fridericia's formula (QTcF) intervals.

All ECGs should be assessed by the investigator as to whether they are clinically significantly abnormal. Any clinically significant abnormalities in QTc interval detected require triplicate ECG results. At each time point at which triplicate ECG are required, 3 individual ECG tracings should be obtained in succession, no more than 2 minutes apart. The full set of triplicates should be completed within 5 minutes.

Single ECGs should be performed at the time of significant LVEF drop and on occurrence of any cardiorespiratory AEs with no obvious diagnosis. For participants with new or worsening respiratory symptoms (such as dyspnoea or cough), an ECG is recommended, and additionally at the discretion of the investigator if clinically indicated.

Situations in which ECG results should be reported as AEs are described in Section [8.3.5](#).

#### **8.2.5      Echocardiogram/Cardiac MRI**

An ECHO or cardiac MRI scan to assess LVEF will be performed at the visits as shown in SoA. The modality of the cardiac function assessments must be consistent for a given participant (ie, if ECHO is used for the screening assessment for a given participant, then ECHO should also be used for subsequent scans for that participant). The participants should also be examined using the same machine and operator whenever possible, and quantitative measurements should be taken (ie, accurate to 1% and not estimated to 5%).

Left ventricular ejection fraction, end diastolic and end systolic left ventricular volumes should be recorded at each ECHO or cardiac MRI assessment.

Participants experiencing an asymptomatic LVEF reduction or left ventricular systolic dysfunction should be managed according to the algorithm provided in Appendix [H 1](#).

Participants who have a drop in LVEF of  $\geq 10$  percentage points from baseline and to below the LLN at the time of selumetinib discontinuation should, where possible, have a follow-up ECHO or cardiac MRI, ECG, vital signs, and weight performed after 30 days to evaluate the potential for reversibility.

An ECHO or cardiac MRI will also be carried out if a participant develops signs and/or symptoms suggestive of deterioration in left ventricular function/cardiac event.

A further ECHO or cardiac MRI should be performed as part of the assessment package for any cardiorespiratory AE with no obvious diagnosis (obvious causes will be managed in accordance with local clinical practice) and additionally at the discretion of the investigator if clinically indicated.

If a participant has had an ECHO/cardiac MRI scan performed within 4 weeks prior to study intervention discontinuation, the discontinuation visit ECHO/cardiac MRI scan is not required unless clinically indicated.

Situations in which ECHO/cardiac MRI scan results should be reported as AEs are described in Section 8.3.5.

### **8.2.6 Clinical Safety Laboratory Assessments**

Blood and urine samples for determination of clinical chemistry, haematology, and urinalysis will be taken at the visits indicated in the SoA.

Additional safety samples may be collected if clinically indicated at the discretion of the investigator. The date, time of collection, and results (values, units and reference ranges) will be recorded on the appropriate eCRF.

The clinical chemistry, haematology, and urinalysis will be performed at a local laboratory at or near to the investigator site. Sample tubes and sample sizes may vary depending on laboratory method used and routine practice at the site.

Urine microscopy will be assessed if other urinalysis measurements are abnormal or if clinically indicated.

Other safety laboratory tests include assessment for pregnancy for women of child-bearing potential. A serum pregnancy test is required at screening, following that a urine or serum pregnancy test is acceptable. Pregnancy tests will be performed every cycle throughout the entire exposure period. Pregnancy tests may be performed at the site using a licensed test (urine or serum pregnancy test). Where a pregnancy test is the only assessment for a cycle, a clinic visit is not required as the test may be performed offsite. The site should obtain the test result from the participant prior to the next onsite visit. Abnormal clinically significant laboratory results should be repeated as soon as possible (preferably within 24 to 48 hours).

The following laboratory variables will be measured.

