			C1 D8	C1 D28	C2 D28	C4 D28	C6 D28	C8 D28	C10 D28	C12 D28	C16 D28	C20 D28	C24 D28 w	C30 b D28 onwards			
Study Day	Day – 28 to Day – 1	Day 1	Day 8	Day 28	Day 56	Day 112	Day 168	Day 224	Day 280	Day 336	Day 448	Day 560	Day 672				
Window (days)			Day 4-14	± 3	± 3	± 7	± 7	± 7	± 7	± 7	± 7	± 7	± 7	± 7	+ 7	+ 7	
PK blood samples u			X														8.5.1
AEs v	X	X	←	=====	=====	=====	=====	=====	=====	=====	=====	=====	=====	→			8.3
Concomitant medication/ procedures	X	X	←	=====	=====	=====	=====	=====	=====	=====	=====	=====	=====	=====	→		6.5

a The 28-day screening period will commence on the date the ‘Screening Visit’ transaction is registered in IRT system. Visit schedule should always be calculated in relation to C1D1. Visits should not be skipped or overwritten in IRT. If a visit (+ visit window) is missed, the visit should be completed as the earliest opportunity. If there is a long gap between the scheduled and actual visit, please check with global study team how visits are to be recorded.

b From Cycle 30 onwards, for all participants remaining on study intervention, assessments will be performed every 6 cycles with the exception of ophthalmic assessments (see footnote l) and pregnancy assessments (see footnote m).

c The EoT visit will be performed for participants who permanently discontinue study intervention for any reason (except for death, lost to follow-up or withdrawal of consent). The EoT visit should be performed as soon as possible after the decision to discontinue treatment permanently has been made. If EoT is >30 days after last treatment dose, then the EoT assessments can also function as the 30-Day Safety follow-up visit.

d Screening tests should be performed within 28 days before the first administration of study intervention, unless otherwise indicated. Written informed consent and any locally required privacy act document authorisation must be obtained prior to performing any protocol-specific procedures, including screening/baseline evaluations.

e Every effort should be made to minimise the time between randomisation and starting treatment (maximum interval of 3 business days of randomisation).

f Assessment of baseline disease characteristics includes documenting location of the target and non-target PN (if applicable) and any PN-related symptoms and results of any previous genetic testing for NF1.

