- l The modality of the cardiac function assessments must be consistent for a given participant. The participant should be examined using the same machine and operator throughout the study wherever possible. Echocardiogram/cardiac MRI is not required at EoT visit if the participant has had an echo/cardiac MRI within 4 weeks prior to study intervention discontinuation, unless clinically indicated. Echocardiogram/cardiac MRI is only required at 30 day safety follow-up in participants who have abnormal findings at the time of selumetinib discontinuation/ EoT visit. Participants who have a drop in LVEF of  $\geq 10$  percentage points from baseline and to below the LLN at the time of selumetinib discontinuation should have a Follow-up ECHO or cardiac MRI, ECG, vital signs, and weight performed at the 30 day safety follow-up.
- m Ophthalmologic assessments may be performed more often, if clinically indicated. After 12 cycles, ophthalmological assessment will be performed every 12 cycles. Only required at the Safety Follow-up visit if abnormal findings at EoT assessment.
- n Pregnancy testing will be performed at screening, Cycle 1 Day 1, and every cycle throughout the entire exposure period, in women of childbearing potential only. A serum pregnancy test is required at screening, following that a urine or serum pregnancy test is acceptable. Where a pregnancy test is the only assessment for a cycle, a clinic visit is not required as the test may be performed offsite. The site should obtain the test result from the participant prior to the next onsite visit.
- o Temperature (same method to be used throughout the study), pulse rate, oxygen saturation by pulse oximetry, respiratory rate, and BP will be assessed. Assessments of BP and pulse rate should be assessed in a sitting position and preceded by at least 5 minutes of rest in a quiet setting without distractions (eg, television, cell phones). Manual techniques will be used only if automated devices are not available. The average of 3 BP readings, taken consecutively at intervals of at least one minute apart will be recorded on the eCRF.

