u Blood samples to measure selumetinib and N-desmethyl selumetinib metabolite will be collected on Cycle 1 Day 8: Pre-Dose, 0.5 h, 1.5 h, 3 h, 6 h and 8 h post-dose. For operational reasons the PK sampling can take place on any day between Day 4 and Day 14 as long as the participant has received 3 consecutive days of dosing immediately prior to the PK day. Every effort should be made to conduct PK sampling within the Day 4 to Day 14 window. However, if for unforeseen reasons this is not possible, PK sampling can be performed ideally within the first cycle but no later than Cycle 12, provided the participant has received 3 consecutive days of dosing immediately prior to the PK day. The selumetinib dose dates and times must be recorded accurately on the day preceding the PK sample day and on the PK sample day.

v Adverse events will be collected from the time of signing the ICF, throughout the treatment period, and including the follow-up period. Adverse events will also be collected at additional telephone assessments on Cycle 3, Day 28; Cycle 5, Day 28; and Cycle 7, Day 28; Cycle 9 Day 28 and Cycle 11 Day 28, as per [Table 2](#).

w From the end of Cycle 24 (Cycle 25 Day 1) participants will not be required to continue to observe the fasting restriction, i.e participant can eat at any time point in relation to each selumetinib intake.

Each treatment cycle is 28 days. Assessments will be performed at the end of each cycle. Study intervention will be dispensed after all assessments have been performed and evaluated by the investigator. Participant's second dose on the day of their on-site visit can be taken from newly dispensed study intervention. Treatment will not be held while end of cycle evaluations are ongoing. Note: Data collection following study analysis until the end of the study is described in Section 8.

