#### **8.3.13.1    Maternal Exposure**

If a participant becomes pregnant during the course of the study, selumetinib should be discontinued immediately.

Pregnancy itself is not regarded as an AE unless there is a suspicion that the study intervention under study may have interfered with the effectiveness of a contraceptive medication.

Congenital anomalies/birth defects and spontaneous miscarriages should be reported and handled as SAEs. Elective abortions without complications should not be handled as AEs. The outcome of all pregnancies (spontaneous miscarriage, elective termination, ectopic pregnancy, normal birth, or congenital anomaly/birth defect) should be followed up and documented even if the participant was discontinued from the study.

If any pregnancy occurs in the course of the study, then the investigator or other site personnel informs the appropriate AstraZeneca representatives within one day, ie, immediately but **no**

**later than 24 hours** of when he or she becomes aware of it.

The designated AstraZeneca representative works with the investigator to ensure that all relevant information is provided to the AstraZeneca Patient Safety data entry site within one or 5 calendar days for SAEs (see Section 8.3.12) and within 30 days for all other pregnancies.

The same timelines apply when outcome information is available.

The PREGREP module in the eCRF is used to report the pregnancy and the PREGOUT is used to report the outcome of the pregnancy.

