4.2.12 PII-pNF Pain Interference Total Score

4.2.12.1 Definition

The PII-pNF assesses the extent to which PN pain interferes with daily functioning. All items ask the patient to consider the pain related to their PN in the past 7 days. Patients are asked how much their PN pain has made it hard for them to engage in physical activities (e.g., challenging physical activities and self-care), affected their physiological processes (e.g., sleep and energy) or impacted their social-emotional functioning (e.g., enjoyment of activities and mood). Items are rated on a 7-point Likert scale (from 0 = not at all to 6 = completely), and the total score is the mean of the completed items.

The PII-pNF is planned to be collected at the end of Cycles 1, 2, 4, 6, 8, 10, and 12 during the randomised period and at Cycles 16, 20, 24, 30, and every 6 cycles onwards.

The randomised period is defined in Section [3.3.2.2](#).

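### Pregnancy is tested every cycle, but the site's only deadline for an offsite result is the next onsite visit, up to 84 nominal days away after Cycle 12 and 140 after Cycle 24

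*Protocol*

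**What the plan says.** **Testing.** Protocol Section 8.2.6 states: "Pregnancy tests will be performed every cycle throughout the entire exposure period". Table 1 footnote n says the same: "every cycle throughout the entire exposure period, in women of childbearing potential only".

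**Offsite tests.** Section 8.2.6 adds: "Where a pregnancy test is the only assessment for a cycle, a clinic visit is not required as the test may be performed offsite". The deadline follows: "The site should obtain the test result from the participant prior to the next onsite visit". Footnote n repeats this. Neither place gives a number of days.

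**Visits.** The footnotes to Table 1 set the calendar: "Each treatment cycle is 28 days. Assessments will be performed at the end of each cycle". After Cycle 12 the onsite columns are Cycles 16, 20, 24 and 30. Footnote b continues: "From Cycle 30 onwards, for all participants remaining on study intervention, assessments will be performed every 6 cycles". SAP Section 4.2.12.1 lists the same visits for a questionnaire completed in clinic: "at Cycles 16, 20, 24, 30, and every 6 cycles onwards".

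**Other contact.** Table 2 schedules telephone assessments at Cycles 3, 5, 7, 9 and 11 only. They cover pain medication, adverse events and concomitant medication or procedures. There is no pregnancy item.

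**Action on pregnancy.** Section 8.3.13.1 states: "If a participant becomes pregnant during the course of the study, selumetinib should be discontinued immediately". Its 24-hour reporting period runs from the moment site staff become aware. Section 7.1 includes pregnancy in a list of situations in which stopping study intervention is permitted, which is weaker wording.

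**The concern.** The deadline for learning a result follows the visit calendar, while the test follows the cycle. Up to Cycle 12 the two nearly coincide. After Cycle 12 they separate, and three other things in the plan make the separation matter.

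- Placebo participants cross over after Cycle 12 (Section 6.1.1), so every woman still on study intervention is then taking selumetinib.
- Study intervention is dispensed at onsite visits (Table 1), so she holds a supply for four to six cycles with no scheduled site contact in between.
- Amendment 1 (Appendix M) moved pregnancy testing from each visit to every cycle because this adult population includes women who can become pregnant. If results need only reach the site by the next visit, a compliant site can still learn them at visit intervals, and much of the gain is lost.

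Until the site has the result it cannot act on Section 8.3.13.1, and the 24-hour report does not start. The stake is participant and fetal safety and the timeliness of pregnancy reporting. No efficacy endpoint is affected.

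**Working it through.** The check is calendar arithmetic.

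**Inputs**
- Cycle length 28 days, assessments at the end of the cycle (Table 1 footnotes).
- Onsite visits at Cycles 1, 2, 4, 6, 8, 10, 12, 16, 20, 24 and 30, then every 6 cycles (Table 1).
- Visit window of ±7 days at the later visits (Table 1).
- Result due before the next onsite visit (Section 8.2.6, footnote n).

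**Reproducing the plan's own days.** End-of-cycle day = 28 × cycle number. This returns all ten end-of-cycle days printed in Table 1: 28, 56, 112, 168, 224, 280, 336, 448, 560 and 672. Cycle 30 has no printed day; the formula gives 28 × 30 = 840.

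**Longest permitted lag** = day of the next onsite visit − day of the first offsite test after the previous visit.

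| Gap between visits | First offsite test | Next visit | Longest lag | With visit 7 days late |
|---|---|---|---|---|
| Cycle 2 to 4 (likewise up to Cycle 12) | Cycle 3, Day 84 | Day 112 | 28 days | 35 days |
| Cycle 12 to 16 (likewise 16 to 20, 20 to 24) | Cycle 13, Day 364 | Day 448 | 84 days | 91 days |
| Cycle 24 to 30 (likewise each later gap) | Cycle 25, Day 700 | Day 840 | 140 days | 147 days |

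**Later tests in the same gap.** After Cycle 12 the three offsite tests have permitted lags of 84, 56 and 28 days. After Cycle 24 the five have 140, 112, 84, 56 and 28 days.

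**Share of tests that may be offsite.** Cycles 13, 14 and 15 out of 13 to 16, so 3 of 4. Cycles 25 to 29 out of 25 to 30, so 5 of 6.

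**Sensitivity to the test day.** The plan fixes the test only to the cycle, and the table assumes Day 28. If the test were done on the first day of the cycle, the lags would be 448 − 337 = 111 days and 840 − 673 = 167 days.

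**Cross-reference.** Footnote b exempts pregnancy tests from the six-cycle schedule and points to footnote m. Footnote m covers ophthalmology; the pregnancy footnote is n. From Cycle 30 on, when the gaps are longest, the reader is sent to the wrong note.

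**The case against.** A reader might infer four stronger things, and the documents support none of them.

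1. **That nobody knows of the positive test for months.** Section 8.2.6 has the site obtain the result from the participant, so she may well have it first. The lag is in the site's knowledge. Continued dosing for months would also require that she knows, keeps taking study intervention and does not call.

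2. **That Sections 8.2.6 and 8.3.13.1 contradict each other.** Both can be followed. One sets the latest time for collecting a result, the other the action once pregnancy occurs. Nothing stops a site from collecting results every cycle. The 24-hour period counted from awareness is also how the protocol treats serious adverse events, overdose and medication error, so it is not a separate fault.

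3. **That 84 and 140 days are typical.** They apply to the first offsite test in each gap when the site waits as long as it may.

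4. **That participants are never told to report a positive test.** The consent text was not available for this review and may contain such an instruction. No such instruction appears in the protocol text reviewed.

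Other text points towards prompt handling. Section 8.2.6 wants clinically significant abnormal results repeated quickly, preferably within 24 to 48 hours. Section 7.1 asks that the participant be told to contact the site if study intervention is stopped. The contraception rules (Section 5.1, Appendix F) should make pregnancy rare.

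These points limit the claim but do not remove it. A repeat test presupposes that the site knows the first result. The Section 7.1 contact is tied to stopping treatment, not to a positive test. Contraception lowers how often the situation arises, not how long the site may wait when it does.

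**Conclusion.** The point holds as a gap between rules. The collection deadline permits the site to remain unaware of a positive offsite test for at most 84 nominal days after Cycle 12 and at most 140 after Cycle 24, plus up to 7 days for the visit window, against about 28 days before Cycle 12. A rule that allows this does not support Section 8.3.13.1 or the purpose that Amendment 1 gave for testing every cycle. The permissive wording on pregnancy in Section 7.1 adds a second inconsistency.

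The figures assume Day 28 tests, visits at their nominal days and a site that uses the full time allowed. They say nothing about how often a delay would occur. The conclusion would weaken if the consent text requires the participant to report a positive test promptly, although the protocol would still need to agree with it. The matter is worth correcting for safety oversight and does not bear on the trial's efficacy conclusions.

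**What to change.** Reconcile Protocol Sections 7.1, 8.2.6 and 8.3.13.1, Table 1 footnote n and Table 2, so that the timing for obtaining each offsite result is consistent with testing every cycle and with Section 8.3.13.1. Check the consent text on the same point. Correct footnote b so that its pregnancy cross-reference leads to footnote n. The interval, and the clinical rule on pregnancy, are for the sponsor to choose.

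The cost is a text clarification and, at most, a brief remote contact or ePRO entry in cycles without a visit, for women of childbearing potential only.
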